2 PROTOCOL AMENDMENT/REVISION HISTORY

| Protocol Version/ Date | Type of Amendment | Amendment Rationale | Sections Affected | Summary of Amendment / Changes to the Protocol |
|-----------------------------|----------------------|---|---|--|
| V1.0 26 May 2021 | N/A | N/A | N/A | N/A – Initial Version |
| V2.0, 22 June 2021 | N/A | Response to MHRA Grounds for Non- Acceptance | Section 8.5 – Toxicology Section 10.3.4 - Progression from Dose Leader Group/Dose Escalation Stopping Criteria Section 10.8.7 – Selection of Doses in the Study | 
 - Section updated to include reference to pre-defined exposure limits for C_{max} & AUC_{0-24} as per MHRA request. - Stopping criteria for systemic exposure updated to include reference to pre-defined exposure limits for C_{max} & AUC_{0-24} as per MHRA request. - Additional text included as per MHRA request to clarify planned study doses in the context of the estimated human pharmacodynamic range. |
| V3.0, 22 October 2021 | Non-Substantial | To align with latest version of Simbec-Orion protocol template | Section 3 – Synopsis Section 5 – Abbreviations Section 8.2 – Physical, Chemical and | 
 - Changes implemented to align with main body text - Abbreviations' list updated to include additional abbreviations to align with latest version of Simbec-Orion template - Capsule size updated from size 3 to size 2 |

| | | | |
|--|--|---|---|
| | | Pharmaceutical Properties and Formulation Section 8.8 - Coronavirus Disease 2019 (COVID-19) Risk/Benefit Assessment Section 10.3.1 – Dose Escalation Procedures | 
- Full definition of NHS, PPE & IMP added- Removal of term 'accrual' in relation to dose escalation for review of PK and safety data.- Removal of term 'pharmacist' and replaced with 'IMP Management team'- Addition of text to confirm that receipt of the signed dose escalation approval form will trigger the release of the IMP for the next dose level to the clinic. |
| | | Section 10.5 – Selection of Study Population Section 10.5.1 – Inclusion Criteria | 
- Full definition of SI added- Criterion #11 updated to include full definition of QTcF- Criterion #12 updated to replace 'pulse' with 'heart rate' as per latest version of Simbec-Orion protocol template |

| | | | | |
|--|--|--|---|---|
| | | | 
Section 10.6.1 – Contraception
 
Section 10.8.2 – Receipt and Storage & Section 10.8.3 – Assembly and Release
 
Section 10.8.11 - Blinding
 | 
– Criterion #16 updated to include full definition for RT-PCR- Statement added to vasectomised partner contraception method to note that if there is no documentation to support the absence of sperm in the ejaculate, then condoms will still be required for these individuals.- Full definition of API added.- Revision of term ‘The Pharmacy’ to ‘IMP Management’- Removal of reference to specific Simbec-Orion SOP numbers and replaced with ‘Simbec-Orion SOPs.’- Revision of storage conditions for IMP from quarantine in a segregated, study specific area within the pharmacy to quarantine within a GMP area to facilitate circumstances where IMP may be stored within the clinical unit or other areas as needed.- Revision of term ‘pharmacist’ to ‘IMP |
|--|--|--|---|---|

| | | | | |
|--|--|---|--|---|
| | | | | Management' or 'team' where relevant. |
| | | Table 10.9.1 – Study Flow Chart – Part A Single Ascending Dose | | - Footnote #8 updated to replace 'pulse' with 'heart rate' as per latest version of Simbec-Orion protocol template |
| | | Table 10.9.2 – Study Flow Chart – Part B Food Effect | | - Footnote #8 updated to replace 'pulse' with 'heart rate' as per latest version of Simbec-Orion protocol template |
| | | Table 10.9.3 – Study Flow Chart – Part C Multiple Ascending Dose | | - Footnote #9 updated to replace 'pulse' with 'heart rate' as per latest version of Simbec-Orion protocol template |
| | | Section 10.9.2.4 - COVID-19 PCR Testing | | – Full definition of RT-PCR removed |
| | | Section 10.9.2.5 - Drug of Abuse and Alcohol | | – Full definition of DOA removed |
| | | Section 10.9.5.1 – Adverse Events | | – Full definition of SI removed |
| | | Section 10.9.5.1.1 – Recording of Adverse Events | | – Full definition of SAE removed |
| | | Section 10.9.7 - Other Safety Assessments & Section 10.11.2 – Study Variables/Endpoints & | | – Vital signs parameters updated to replace 'pulse' with 'heart rate' as per latest version of Simbec-Orion protocol template |

| | | | Appendix 1 – Normal Ranges for Vital Signs and ECG Parameters | |
|----------------------------|-------------|-------------------------|--|--|
| V4.0 14/January 2022 | Substantial | Updates to study design | Protocol Section 3 – Synopsis Protocol Section 5 – Abbreviations Protocol Section 8.8 - Coronavirus Disease 2019 (COVID-19) Risk/Benefit Assessment Protocol Section 10.2 – Adaptive Elements Protocol Section 10.5.1 – Inclusion Criteria Table 10.9.1, 10.9.2, 10.3.3 – Study Flow Charts Protocol Section 10.9.6 – COVID-19 Testing | Risk/benefit assessment updated to reflect the requirement for all participants enrolled into the study to be fully vaccinated against COVID-19 as per the current Welsh/UK Government guidelines Adaptive design elements updated to indicate that the timing of exploratory PD samples in both Part A and Part C. Criterion #16 updated New criterion #17 Flow chart updated to include timepoints for exploratory PD sampling Part C flow updated to capture additional COVID-19 tests Section updated to reference routine performance of Lateral Flow Testing |

| | | | |
|--|--|--|---|
| | | Table 10.9.4, 10.9.6 Summary of Blood Volumes Protocol Section 10.9.26 – Other Assessments Protocol Section 10.10.1 - Summary of Source Documentation Location Protocol Section 10.11.2 – Study Variables/Endpoi nts Protocol Section 10.11.8 – PK Data | Blood volume updated to reflect addition of exploratory PD samples New section added to describe the procedures for collection of exploratory PD samples Addition of reference to PD sample collection Endpoints for derived plasma PK for all study parts updated to include AUC0-24 Text updated to include AUC0-24 |
|--|--|--|---|

3 SYNOPSIS

| |
|---|
| NAME OF COMPANY: Artax Biopharma Inc |
| NAME OF INVESTIGATIONAL MEDICINAL PRODUCT: AX-158, Placebo |
| NAME OF ACTIVE INGREDIENT: AX-158 |
| TITLE OF STUDY: A Randomised, Double-blind, Placebo-controlled, Study of the Safety, Tolerability, and Pharmacokinetics of AX-158 Following Administration of Single and, Multiple Ascending Oral Doses and Food Effect sub-study in Healthy Male Volunteers. |
| PRINCIPAL INVESTIGATOR: [name] |
| STUDY CENTRE: Simbec-Orion Clinical Pharmacology [name], UK |
| CLINICAL PHASE: I |
| OBJECTIVES: Primary Objective 
• To assess the safety and tolerability of single and multiple ascending doses of AX-158 when administered to healthy participants (Part A and Part C). Secondary Objective 
• To investigate the PK of single and multiple doses of AX-158 in healthy participants (Part A and Part C).• To investigate any food effect on the PK of AX-158 following oral administration of a single dose to healthy participants (Part B). |
| METHODOLOGY: This is a phase I, randomised, double-blind, placebo-controlled study to investigate the safety, tolerability, and PK of AX-158 in healthy male participants following single (Part A) and multiple (Part C) ascending doses including food effect (Part B). The study will be conducted in three parts (Part A, Part B and Part C). Part A (SAD) will enrol 8 participants per cohort randomised (3:1) to receive AX-158 (6 participants) or placebo (2 participants). Part A will follow a single ascending dose (SAD) design with all participants receiving one dose of AX-158 (or placebo) in the fasted state. Part B (Food Effect) will be conducted in 8 participants in a cross-over manner; each participant will receive AX-158 in the fed and fasted state. Part C (MAD) will enrol 8 participants pre cohort randomised to (3:1) to receive AX-158 (6 participants) or placebo (2 participants). Part C will follow a multiple ascending dose (MAD) design with participants receiving AX-158 (or placebo) once daily for 10 consecutive days, in a fed or fasted state (depending on the outcome of the Part B (Food Effect). Doses, dosing duration and dose regimen (i.e., q.i.d., b.i.d., t.i.d.) of AX-158 and matching placebo for Part C may be modified based on all available safety, tolerability, and PK data and applied to additional MAD cohorts. Each participant will participate in only one cohort and in one of the study parts. Part A (SAD) will be conducted in up to forty (40) participants (5 cohorts of 8 participants). An additional two cohorts of eight (8) participants each (up to 16 additional participants total) may be investigated if required. Part B (Food Effect) will be conducted in 8 participants in a cross-over manner. Part C (MAD) will be conducted in up to twenty-four (24) participants (3 cohorts of 8 participants). An additional two cohorts of eight (8) |

participants each (up to 16 additional participants total) may be investigated if required. Each participant will be assigned to only one study part and within each part, assigned to one cohort.

Participants in Part A (SAD) will undergo a screening period (Day -28 to Day -2), an in-house treatment period comprising 4 overnight stays (from Day -1 to Day 4) and a follow up visit 5-7 days following administration of AX-158 or placebo.

Participants in Part B (Food Effect) will undergo a screening period (Day -28 to Day -2), two in-house treatment periods comprising of 4 overnight stays (from Day -1 to Day 4) separated by a minimum of 7 days between doses and a follow up visit 5-7 days following the final administration of AX-158.

Participants in Part C (MAD) will undergo a screening period (Day -28 to Day -2), an in-house treatment period comprising 13 overnight stays (from Day -1 to Day 13) and a follow up visit 5-7 days following the final administration of AX-158 or placebo.

This study is designed to be adaptive, and the following elements may be revised based on emerging clinical safety and PK data during the course of the trial without a substantial amendment:

- Following review of the Part B Food effect cohort PK data, participants in Part C cohorts may be administered AX-158 under fasted or fed conditions, as deemed appropriate, pending DERC determination of any appreciable impact of food effect of AX-158. If food effect is seen, cohorts in Part C could be dosed with a standardised meal (as opposed to the high-fat breakfast). This decision will be documented in the Food Effect Cohort Dose Escalation Review meeting minutes.
- The timing, type, and number of safety, PK assessments may be modified (without extending the duration of the study).
- A minimum washout of 7 days is expected within Part B but may be extended based on emerging safety and PK data to 14 days.
- The number and/or volume of blood samples per assessment may be increased as long as the total volume of blood drawn for a participant does not exceed 10% of the pre-specified total blood volume or surpass 500 mL (except when extra blood samples need to be taken for safety reasons).
- In Part C (MAD), it is planned to dose AX-158 or placebo once daily for at least 10 consecutive days; doses dosing duration and dose regimen (i.e., q.i.d., b.i.d, t.i.d) of AX-158 and matching placebo for Part C may be modified based on all available safety, tolerability, and PK data and applied to additional MAD cohorts up to a maximum of 14 days.
- Dose levels/dosing regimen may be adjusted lower based on emerging safety and PK data.
- Additional dose level(s) may be examined if deemed safe and appropriate. These cohorts will enrol 8 participants (for SAD cohorts) and up to 8 participants (for MAD cohorts).
- Currently it is planned that in order to dose escalate between cohorts and between study parts, PK data from up to the 24 hr post-last time point in all parts and 72 hr post-last dose safety data is required. However, if during the course of dose escalation, it is determined necessary to do so, then dose escalation procedures may be extended in order to include additional PK data up to the 72 hr post-last dose time point in all study parts.
- Exploratory PD samples will be taken pre-dose in Part A (SAD) and Part C (MAD) additional sample(s) will be taken based on emerging data. The total blood volume will not exceed 500mL.

The clinical phase is anticipated to take place between Q3 2021 (first participant first visit) and Q2 2022. The conclusion of the study is defined as last participant last visit (in Part C). The study will take place in the Clinical Unit of Simbec-Orion Clinical Pharmacology under full medical and nursing supervision.

A schedule of all study assessments is provided in [Table 10.9.1](#) (Part A SAD), [Table 10.9.2](#) (Part B Food Effect) and [Table 10.9.3](#) (Part C MAD).

NUMBER OF PARTICIPANTS:

Up to 104 healthy male participants may be enrolled into the study.

- Part A: 40 participants (5 cohorts of 8 participants each). An additional 2 cohorts of 8 participants each may be investigated if required (max. 16 additional participants).
- Part B: 8 participants (1 cohort of 8 participants).
- Part C: 24 participants (3 cohorts of 8 participants each). An additional 2 cohorts of 8 participants each may be investigated if required (max. 16 additional participants).

MAIN INCLUSION CRITERIA:

1. Healthy Male participant, between 18 and 50 years of age, inclusive.
2. Male participant (and partner of childbearing potential) willing to use a highly effective method of contraception in addition to a condom, if applicable (unless anatomically sterile or where abstaining from sexual intercourse is in line with the preferred and usual lifestyle of the participant) from first dose until 4 months after last dose of IMP.
3. Participant with a body mass index (BMI) of 18-30kg/m².
BMI = body weight (kg) / [height (m)]².
4. No clinically significant history of previous allergy / sensitivity to AX-158 or any of the excipients contained within the IMP.
5. Participant with no history of autoimmune disease, cardiac disease, kidney disease or any food intolerance.
6. No clinically significant abnormal test results for serum biochemistry, haematology and/or urine analyses within 28 days before the first dose administration of the IMP.
7. Total serum bilirubin, alkaline phosphatase (ALP), aspartate transaminase (AST) and alanine transaminase (ALT) $\leq 1.5 \times$ upper limit of normal (ULN). If total bilirubin is above the upper limit of normal and is then fractionated, direct bilirubin must be within normal limits.
8. Total serum Testosterone levels 2 x above the lower limit of the normal range within 28 days before the first dose administration of the IMP.
9. Participant with a negative urinary drugs of abuse (DOA) screen (including alcohol) test results, determined within 28 days before the first dose administration of the IMP (N.B.: A positive test result may be repeated at the Investigator's discretion).
10. Participant with negative human immunodeficiency virus (HIV), hepatitis B surface antigen (HBsAg) and hepatitis C virus antibody (HCV Ab) test results at Screening.
11. No clinically significant abnormalities in 12-lead electrocardiogram (ECG) determined within 28 days before first dose of IMP including a QRS > 120ms, PR interval > 220ms and QT interval corrected using Fredericia's formula (QTcF) > 450ms.
12. No clinically significant abnormalities in vital signs (e.g., blood pressure/heart rate, respiration rate and oral temperature) determined within 28 days before first dose of IMP.
13. Participant must be available to complete the study (including all follow-up visits).
14. Participant must satisfy an Investigator about his fitness to participate in the study.
15. Participant must provide written informed consent to participate in the study.
16. Participants with a negative COVID-19 test on admission.
17. Participants who are considered fully vaccinated to COVID-19 as per the current Welsh/UK Government guidelines.

MAIN EXCLUSION CRITERIA:

1. A clinically significant history of gastrointestinal disorder likely to influence IMP absorption.

2. Use of prescription or non-prescription drugs, including vitamins, herbal and dietary supplements within 28 days or 5 half-lives (whichever is longer) prior to the first dose of IMP. Occasional use of paracetamol will be allowed.
3. Evidence of renal, hepatic, central nervous system, respiratory, cardiovascular, or metabolic dysfunction.
4. A clinically significant history of drug or alcohol abuse (defined as the consumption of more than 14 units [for male and female participants] of alcohol a week) within the past two years.
5. Inability to communicate well with the Investigators (i.e., language problem, poor mental development, or impaired cerebral function).
6. Participation in a New Chemical Entity (NCE) clinical study within the previous 3 months or five half-lives, whichever is longer, or a marketed drug clinical study within the 30 days or five half-lives, whichever is longer, before the first dose of IMP. (*Washout period between studies is defined as the period of time elapsed between the last dose of the previous study and the first dose of the next study*).
7. Donation of 450 mL or more blood within the 3 months before the first dose of IMP.
8. Vegans, vegetarians, or other dietary restrictions (e.g., restrictions for medical, religious, or cultural reasons, etc), which would prevent participants from consuming a high-fat breakfast or standardised meal.
9. Users of nicotine products i.e., current smokers or ex-smokers who have smoked within the 6 months prior to screening or users of cigarette replacements (i.e., e-cigarettes, nicotine patches or gums).
10. Participants who have received a COVID-19 vaccine injection within 28 days prior to the first dose of IMP.

IMP ADMINISTRATION:**Part A**

The following IMPs will be administered:

- AX-158 capsules
- Matching placebo

The IMPs will be administered fasted (after an overnight fast of at least 10 h) with 240 mL water. More water may be provided (except PK days) if needed and the actual water taken with dose administration will be recorded in the eCRF.

Part B

Each participant will receive the following IMP over 2 treatment periods (1/period) in accordance with the randomisation code:

- AX-158 capsules

The IMP will be administered in either the fed or fasted (after an overnight fast of at least 10h or following consumption of a high-fat breakfast) state in accordance with the randomisation with 240 mL of water. More water may be provided (except PK days) if needed and the actual water taken with dose administration will be recorded in the eCRF.

Part C

The following IMPs will be administered:

- AX-158 capsules
- Matching placebo

The IMPs will be administered fasted (after an overnight fast of at least 10 h) with 240 mL water. More water may be provided (except PK days) if needed and the actual water taken with dose administration will be recorded in the eCRF. Participants must remain sitting for at least 1 h after dose. If food effect is observed, cohorts in Part C could be dosed with a standardised meal (as opposed to the high-fat breakfast).

STUDY VARIABLES/ENDPOINTS:**PK****Part A**

The following plasma PK endpoints will be derived: C_{max} , T_{max} , λz , $t_{1/2}$, AUC_{0-24} , AUC_{0-t} , AUC_{0-inf} , $AUC_{\%extrapolated}$, CL/F , Vz/F .

Part B

The following plasma PK endpoints will be derived: C_{max} , T_{max} , T_{lag} , λz , $t_{1/2}$, AUC_{0-24} , AUC_{0-t} , AUC_{0-inf} , $AUC_{\%extrapolated}$, CL/F , Vz/F .

Part C

The following plasma PK endpoints will be derived on Day 1: C_{max} , T_{max} and AUC_{0-24} , (AUC_{0-t} will also be derived if dosing interval other than q.d.).

The following plasma PK endpoints will be derived on Final Dosing Day: C_{max} , T_{max} , λz , $t_{1/2}$, AUC_{0-24} , (AUC_{0-t} will also be derived if dosing interval other than q.d.), AUC_{0-t} , AUC_{0-inf} , $AUC_{\%extrapolated}$, CL/F and Vz/F .

The following urine PK parameters will be derived on Day 1 and Final Dosing Day: Ae , $Ae\%$, CL_R .

Steady-State: For each dose level, log-transformed trough concentration levels at pre-dose day 5 will be subjected to a mixed effects analysis of variance (ANOVA) with study day as a fixed effect and participant as a random effect in order to establish whether and when steady-state has been attained for each dose level. Back-transformed ratios for the comparisons of each consecutive day (i.e., Day 3/Day 2) will be presented along with corresponding 90 % CI.

Accumulation: For each dose level, log-transformed C_{max} and AUC_{0-t} values on Day 1 and Final Dosing Day (Day 10) will be subjected to an ANOVA with study day as a fixed effect and participant as a random effect. For comparison, point estimates and 90 % CI for the difference between Final Dosing Day (Day 10) and Day 1 will be constructed using the residual mean square error obtained from the ANOVA for each dose level. The point and interval estimates will then be back transformed to give estimates of the ratios of the geometric least squares means and corresponding 90 % CI.

Safety Part A, B and C

- AEs.
- Laboratory safety (biochemistry, haematology, coagulation, and urinalysis).
- Vital signs (systolic/diastolic blood pressure, heart rate, oral body temperature and respiratory rate).
- 12-lead ECG (Heart rate, PR interval, QRS width, RR interval, QT interval and QT interval corrected using Fredericia's formula (QTcF)).

STATISTICAL METHODS:

There will be no formal hypothesis testing. All descriptive statistical analyses will be performed using the most recently released and available SAS® statistical software, unless otherwise noted. Continuous variables will be summarised by descriptive statistics (sample size [n], mean, standard deviation [SD], median, minimum, and maximum). Categorical variables will be summarised in frequency tables (n, frequencies, and percentages). Individual participant data will be presented in listings. Missing data will not be imputed unless otherwise stated. There will be a detailed description of participant disposition; participant demographics and baseline

characteristics will be summarised. PK data will be presented descriptively and graphically. A review of safety data and available preliminary PK data will be conducted by the DERC. A statistical analysis plan (SAP) will fully describe the planned analyses for this study.

| | |
|---------------------------|---|
| DURATION OF STUDY: | Part A: approximately 6 weeks for each individual (from the screening to post-study follow-up). Part B: approximately 8 weeks for each individual (from the screening to post-study follow-up). Part C: approximately 7 weeks for each individual (from the screening to post-study follow-up). |
|---------------------------|---|

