10.11.3 Analysis Sets

Safety Set: All randomised participants who receive at least 1 dose of IMP will be included in the safety analysis.

PK Set: The PK set will include participants who receive IMP (one dose in Part A, both doses in Part B (fed/faasted), up to 10 doses in Part C), have sufficient plasma concentration-time profiles and comply with the following criteria:

- Do not have an occurrence of vomiting (that occurs at or before 2 times median T_{max} within the appropriate cohort or treatment) or diarrhoea which renders the concentration profile unreliable; For Part C this applies to PK sampling days only
- Do not use a concomitant medication which renders the concentration profile unreliable;
- Do not have a Day 1 pre-dose concentration that is greater than 5% of the corresponding C_{max} ;
- Have at least one pharmacokinetic sample with concentration above the lower limit of quantitation (LLOQ);
- Do not violate the protocol in such a way that may invalidate or bias the results (major protocol violators).

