3.1 OVERVIEW

This is a phase I, randomised, double-blind, placebo-controlled study to investigate the safety, tolerability, and PK of AX-158 in healthy male participants following single (Part A) and multiple (Part C) ascending doses including food effect (Part B).

The study will be conducted in three parts:

Part A

Part A (SAD) will enrol up to 8 participants per cohort randomised (3:1) to receive AX-158 or placebo. Part A will follow a single ascending dose (SAD) design with all participants receiving one dose of AX-158 (or placebo) in the fasted state.

This part will be conducted in up to 34 participants (8 participants in cohorts 1 and 5, 6 participants in cohorts 2, 3 and 4). An additional two cohorts of up to eight (8) participants each (up to 16 additional participants total) may be investigated if required.

Part B

Part B (Food Effect) will be conducted in up to 8 participants in a cross-over manner; each participant will receive AX-158 in the fed and fasted state.

This part will be conducted in up to 8 participants in a cross-over manner.

Part C

Part C (MAD) will enrol up to 8 participants per cohort randomised to (3:1) to receive AX-158 or placebo. Part C will follow a multiple ascending dose (MAD) design with participants receiving AX-158 (or placebo) once daily for 10 consecutive days, in a fed or fasted state (depending on the outcome of the Part B (Food Effect)). Doses, dosing duration and dose regimen (i.e., q.i.d., b.i.d., t.i.d.) of AX-158 and matching placebo for Part C may be modified based on all available safety, tolerability, and PK data and applied to additional MAD cohorts.

This part will be conducted in up to twenty-four (24) participants (3 cohorts of up to 8 participants). An additional two cohorts of up to eight (8) participants each (up to 16 additional participants total) may be investigated if required.

Duration of study:

- Part A: approximately 6 weeks for each individual (from the screening to post-study follow-up).
- Part B: approximately 8 weeks for each individual (from the screening to post-study follow-up).
- Part C: approximately 7 weeks for each individual (from the screening to post-study follow-up).

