6.3 PK SET

The PK set will include subjects who receive active IMP (one dose in Part A, both doses in Part B (fed/fasted), up to 10 doses in Part C), have sufficient plasma concentration-time profiles and comply with the following criteria:

- Do not have an occurrence of vomiting (that occurs at or before 2 times median T_{max} within the appropriate cohort or treatment) or diarrhoea which renders the concentration profile unreliable. For Part C this applies to PK sampling days only.
- Do not use a concomitant medication which renders the concentration profile unreliable.
- Do not have a Day 1 pre-dose concentration that is greater than 5% of the corresponding C_{max} .
- Do not violate the protocol in such a way that may invalidate or bias the results (major protocol violators).

For Part C, a subject may be included in the PK Set if they have a valid Day 1 PK profile which meets the above criteria, as the Day 1 PK data can be included in the dose proportionality/independence assessment. For inclusion in the Day 10 dose proportionality/independence assessment, subjects must have fulfilled the above criteria and received all doses of study drug.

In order to be included in the statistical comparisons for Part B, a subject is required to be included in the PK Set for the two treatments being evaluated within the particular comparison.

All protocol deviations within the study database will be reviewed to determine whether they affect a subject's eligibility for inclusion in the PK Set. Any deviations and reasons for exclusion will be identified and documented before statistical analysis of the pharmacokinetic data is undertaken.

This analysis set will be used for PK summaries and statistical analyses.

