11.4.3.2 Part C (MAD) - Dose-Proportionality/Independence

Dose-Proportionality

For Day 1 and Final Dosing Day (Day 10), dose proportionality will be assessed by performing a regression analysis of the log-transformed C_{\max} , AUC_{0-tau} and AUC_{0-inf} (Day 10 only) values versus the log-transformed dose using the power model with a fixed effect for log (dose). For each parameter, a point estimate and 95 % CI will be calculated for the slope of the regression line.

Version: 3.0
Document Title: SAP Template - Phase 1
Document Number: TEMP-00109
Previous Document Number: STATt008

The power model is defined as:

$$\log_e(C_{\max}, AUC_{0-t}, AUC_{0-\infty}) = \alpha + \beta \log_e(\text{Dose}) + \varepsilon,$$

where α is the intercept, β is the slope and ε is the error term.

Geometric LSMeans and associated 95% CIs along with individual subject values for the derived pharmacokinetic parameters C_{\max} , AUC_{0-t} and $AUC_{0-\infty}$ will be presented graphically versus dose with each parameter presented on a separate plot.

Dose Independence

For Final Dosing Day (Day 10), dose independence will be assessed for $t^{1/2}$ and CL/F by performing a regression analysis of the untransformed parameters versus dose with a fixed effect for dose. For each parameter, a point estimate and corresponding 95 % CI will be calculated for the slope of the regression line.

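### The Part C Final Dosing Day power model has no rule for cohorts on different dosing intervals, and the ten-dose PK Set wording does not fit the regimens the plan permits

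*Protocol*

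**What the plan says.** **Adaptive scope.** The protocol Synopsis, repeated in 10.2, lists elements that "may be revised based on emerging clinical safety and PK data during the course of the trial without a substantial amendment". One is the Part C schedule: once daily for at least 10 days as planned, with changes to dose, duration and regimen based on safety, tolerability and "PK data and applied to additional MAD cohorts up to a maximum of 14 days". SAP 3.1 carries the regimen part forward: "Doses, dosing duration and dose regimen (i.e., q.i.d., b.i.d., t.i.d.) of AX-158 and matching placebo for Part C may be modified". At most two additional Part C cohorts are foreseen.

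**PK Set.** Protocol 10.11.3 describes Part C dosing in the set as "up to 10 doses in Part C), have sufficient plasma concentration-time profiles", and SAP 6.3 keeps the phrase. SAP 6.3 adds that "a subject may be included in the PK Set if they have a valid Day 1 PK profile which meets the above criteria". For the Day 10 dose-proportionality and dose-independence models, "subjects must have fulfilled the above criteria and received all doses of study drug".

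**Model.** SAP 11.4.3.2 describes the method, before naming the parameters, as follows: "For Day 1 and Final Dosing Day (Day 10), dose proportionality will be assessed by performing a regression analysis of the log-transformed". The parameters are Cmax, AUC0-tau and AUC0-inf (the last on Day 10 only), modelled against log dose, with log dose the only effect. CL/F and half-life are regressed untransformed on dose. SAP 10.2 and 10.7 plan no covariates and no subgroups.

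**Provision for non-q.d. dosing.** SAP 11.4.2 derives AUC0-tau only for a non-q.d. regimen, yet its Final Dosing Day entry fixes the interval at 24 hours after the Day 10 dose. Table footnotes are to be adapted. Steady state and accumulation are analysed separately by treatment or dose level.

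**The concern.** A power-model slope near 1 is read as dose proportionality. That reading requires the cohorts to differ in dose and nothing else that moves the parameter. After repeated dosing, Cmax and the AUC extrapolated to infinity after the last dose also contain drug carried over from earlier doses, and the carry-over grows as the interval shortens. A b.i.d. cohort in the same regression as q.d. cohorts therefore shifts the slope even when PK is exactly proportional. The shift changes sign according to whether the regressor is the single or the daily dose, which the SAP leaves open. The CL/F regression inherits the problem because SAP 11.4.2 computes CL/F as Dose/AUC0-inf.

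Separately, the ten-dose phrase matches only the planned schedule. Taken as a ceiling, it would remove fully dosed participants in a changed-regimen cohort from the PK summaries and models. Multiple-dose PK is a secondary objective.

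**Working it through.** **1. Dose counts** (administrations per day × days)

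| Regimen | 10 days | 14 days |
|---|---|---|
| q.d. | 10 | 14 |
| b.i.d. | 20 | 28 |
| t.i.d. | 30 | 42 |
| q.i.d. | 40 | 56 |

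The planned schedule reproduces the ten in the PK Set wording. Every permitted extension exceeds it (14 to 56). A b.i.d., t.i.d. or q.i.d. participant passes ten doses on Day 6, 4 or 3. With 6 active participants per cohort, the most that could be affected is 2 × 6 = 12 of 5 × 6 = 30 (40%). That needs both optional cohorts to run, both to change regimen, and the literal reading to be applied.

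**2. Slope when one b.i.d. cohort is pooled**

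Inputs: 10, 20 and 40 mg q.d. plus 40 mg b.i.d., an arithmetic illustration only (Part C doses are not fixed in the documents). Assumptions not in the documents: one compartment, rapid absorption, steady state, true slope 1, half-life 6, 12 or 24 h.

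The accumulation factor is R(τ) = 1/(1 − 2^(−τ/t½)). At steady state, both Cmax and AUC0-inf after the last dose are proportional to unit dose × R(τ). The b.i.d. cohort is therefore raised, relative to q.d. at the same unit dose, by r = R(12)/R(24):

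- 6 h: (1 − 1/16)/(1 − 1/4) = 1.25
- 12 h: (1 − 1/4)/(1 − 1/2) = 1.50
- 24 h: (1 − 1/2)/(1 − 0.707) = 1.71

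*Unit dose as regressor.* In log2 units from 10 mg, x = 0, 1, 2, 2; mean 1.25; sum of squares 2.75; deviation of the fourth cohort 0.75. Slope = 1 + (0.75/2.75) × log2(r).

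*Daily dose as regressor.* x = 0, 1, 2, 3; mean 1.5; sum of squares 5; deviation of the fourth cohort 1.5. Slope = 1 + (1.5/5) × log2(r/2).

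| Half-life | r | Slope, unit dose | Slope, daily dose |
|---|---|---|---|
| 6 h | 1.25 | 1.09 | 0.80 |
| 12 h | 1.50 | 1.16 | 0.88 |
| 24 h | 1.71 | 1.21 | 0.93 |

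**3. CL/F.** As Dose/AUC0-inf with unit dose, the b.i.d. cohort's value relative to q.d. is 1/r: 0.80, 0.67 and 0.59. True clearance is identical, so the regression of CL/F on dose shows a trend that is not there.

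**4. Where the shift does and does not arise.** A second layout used three q.d. cohorts at relative doses 1, 2 and 4 plus two additional cohorts, oral absorption at 1/h, half-life 6 to 48 h and true slope 1:

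- Two 14-day q.d. cohorts: slope 1.000 up to a 24 h half-life, 1.012 at 48 h.
- Two 10-day b.i.d. cohorts at unit doses 2 and 4, per-administration dose: Cmax and AUC0-inf 1.08 to 1.19; steady-state AUC0-tau over the true interval 1.00.
- The same b.i.d. cohorts with the AUC taken over 24 h after the last dose, as SAP 11.4.2 literally states: 1.08 to 1.19. AUC0-tau is free of bias only when the true interval is used.
- The same b.i.d. cohorts against daily dose: Cmax 0.78 to 0.96, AUC0-tau 0.65.
- Two 10-day q.i.d. cohorts at unit doses 1 and 2, per-administration dose: Cmax 0.60 to 0.78.

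Size and direction therefore depend on half-life and on where the changed-regimen cohorts sit in the dose range.

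**The case against.** The strongest reply concerns the PK Set. The ten-dose phrase stands in a parenthesis beside the one dose of Part A and the two of Part B, so it can be read as describing planned dosing and admitting those who took fewer. None of the bulleted criteria sets a maximum. The SAP admits a valid Day 1 profile and, for Day 10, asks for all doses without giving a number. SAP 6 has membership agreed before database lock. A reader might infer that every participant in such a cohort must drop out; the documents do not support that. The ambiguity remains, because the SAP's additions still refer back to the criteria above them.

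A reader might also infer that any changed cohort biases every slope. It does not: step 4 clears longer q.d. dosing for practical purposes, and AUC0-tau over the true interval on unit dose. Steady state and accumulation are not pooled across regimens. Nor does the plan dispense with all amendment; it says only that a substantial one is not needed. SAP 1.1 promises a review of protocol changes for SAP impact, and SAP 10.1 allows alternative methods documented in the study report. The SAP follows protocol version 5.0, whereas the protocol at hand is 4.0. The 14-day limit comes from the latter and is not in the SAP, although the regimen flexibility is.

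Consequences are limited too. The protocol Synopsis rules out formal hypothesis testing, no acceptance limit is attached to the slope, and escalation rests on committee review of the data. These points lower the priority. They do not repair the model: choosing the dose definition and the pooling after the data are seen is what a SAP exists to avoid.

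**Conclusion.** The point holds, conditionally. If a non-q.d. Part C cohort is opened and analysed as written, the Final Dosing Day slopes for Cmax and AUC0-inf and the CL/F regression mix dosing interval with dose. The illustration puts the slope at 1.09 to 1.21 on unit dose or 0.80 to 0.93 on daily dose when the truth is 1. It rests on linear one-compartment PK, an assumed half-life of 6 to 24 h and one particular cohort layout; other layouts change its size and sign. The PK Set wording is inconsistent with the permitted 14 to 56 doses, and the inconsistency creates a risk of exclusion rather than a certain loss. Nothing is affected if every cohort stays on 10 days q.d. Priority is low to moderate.

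**What to change.** - **SAP 11.4.3.2:** fit the Final Dosing Day dose-proportionality and dose-independence models only to cohorts sharing the same dosing interval, and define dose as dose per administration. A 14-day q.d. cohort can stay in the q.d. model. Summarise other regimens descriptively. A regimen term is not a substitute when only one cohort is non-q.d., because it is fully confounded with that cohort, which then adds nothing to the slope.
- **Protocol 10.11.3 and SAP 6.3:** replace the ten-dose phrase with the planned doses of the assigned regimen, keeping the SAP's Day 1 provision. If the protocol is not amended, record the change in SAP 1.2.
- **SAP 11.4.2:** for Final Dosing Day AUC0-tau, replace the fixed 24 hours and Day 10 with the cohort's actual interval and Final Dosing Day.

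The cost is a few sentences, with no new data, and no result changes if all cohorts remain on 10 days q.d. The price of restricting the model is that a lone non-q.d. cohort gives no slope information, which is preferable to a slope that cannot be interpreted.
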